9 DATA COLLECTION AND DATA MONITORING

9.1 CRF and Source Documentation

The site study coordinator will complete interview and demographic case report forms (CRFs) for each subject (see Appendices 1-3). A detailed manual will be provided to each site to assist staff in: 1) obtaining sensitive information by face-to-face questioning; 2) ensuring appropriate coding of the questionnaire responses; and 3) ensuring correct completion of the CRF. Instructions for administration of interviews, completion of CRFs, and submission of data will be discussed at a training session prior to the beginning of the study.

All data recorded on the study forms must be legible and recorded in black ink or typed. Data errors are not to be erased, removed with "white out," or completely blackened over; rather, one line should be drawn through the error, the correction entered near by, and the entry initialed and dated by the Site Principal Investigator or study coordinator.

The paper questionnaire forms completed for each subject will be retained in a secure location in each clinical site as the primary source document.

When required information has not been provided, an explanation should be provided in a comments section of the CRF.

CRF data must be well maintained and up-to-date. The questionnaire portion of the CRF should be completed in hard copy during the interview, and the demographic portion of the CRF should be completed within one week of the interview.

Subjects will be identified by CSCC subject numbers assigned at enrollment. Names and other identifiers will not appear on any study documents.

9.2 Data Management

The Statistics and Data Management Center (SDMC), which is Rho Federal Systems Division, Inc., located in Chapel Hill, North Carolina, will provide statistical and data management support for this study. Responses to interview and demographic CRFs will be entered into a web-based data collection system by CSCC Center Staff within one week of the visit at which the data were collected. The data collection system will be developed and maintained by the SDMC.

9.3 Data Monitoring

After study initiation, individual sites will monitor CRFs and source documents for accuracy, protocol compliance, subject safety, and adherence to guidelines outlined in the CSCC Manual of Procedures.

9.4 Timeline

To PRC for review of study materials	October 2004
PRC approval	November 2004
Negotiate study budget	November 2004
To DSMB for review of study materials	January 2005
Final DSMB Approval	March 2005
Distribution of Informed Consent Templates to sites	April 2005
Negotiate study budget	May 2005
Interviewer Training	May 2005
Pilot testing	June 2005
Finalize Case Report Forms and EDC system	July 2005
EDC Training	July 2005
Enrollment begins	July 2005

It is anticipated that enrollment should be rapid. If most clinical Centers see 50 total patients per week, 40% of whom are male (as males may be less likely to present for comprehensive care), there will be 20 potential subjects per week per Center. Excluding the subjects under age 5 who may be half of all subjects in pediatric Centers, this allows 10 potential subjects per Center per week. Clinical time considerations, age/genotype stratification of the study, or patient preference may exclude half of the eligible subjects, allowing conservatively 5 subjects per Center per week. If all 10 Centers participate, this would allow 50 subjects into the study every week. This is especially true since there are 10 Centers in the CSCC, but several of the Centers have more than one site. Total planned accrual is 1,650 subjects, which should be achievable in 33 weeks of full enrollment. Given the realities of beginning a study in a large number of Centers, and the relative scarcity of older patients relative to younger ones, it is anticipated that it may take up to twice this long from the date of first subject enrollment to full accrual.

10 STATISTICAL ANALYSIS

10.1 Sample Size

Approximately 1,650 questionnaires will be completed by patients cared for in all participating institutions. Fourteen hundred of these will be from subjects with sickle cell anemia (HbSS) or the clinically similar sickle beta zero thalassemia (HbS β^0). Prior studies of prevalence have suggested that priapism is most common in patients with HbSS, and this work has provided the data for the hypothesis of prevalence in this study. All statistical considerations detailed below apply to the 1,400 HbSS/HbS β^0 questionnaires.

An additional 250 questionnaires from males with sickle beta plus thalassemia (HbS β^+) and sickle hemoglobin C disease (HbSC) will also be obtained and evaluated descriptively. This sample will not allow for a statistical estimate of priapism prevalence; rather, this analysis will be descriptive and provide information for case study. It will also suggest a rationale for inclusion or exclusion of patients with these disorders in subsequent intervention trials.

Survey numbers will be stratified by age using previously reported[1,14] frequencies of priapism in different age groups. In a survey of pediatric sickle cell anemia patients whose methodology closely matches that of this study, the actuarial cumulative frequencies of priapism at different ages were reported as: 12.9% \pm 4.1% by 10 years of age, 50.3% \pm 8.5% by 15 years of age, and 89.3% \pm 9.0% by 20 years of age[1]. A survey of adult patients with all genotypes of sickle cell disease disclosed a frequency of 35% of the population at a mean age of 22 years.[14] Clearly there is some recall bias in adult patients for an event that could have happened decades earlier.

Enrollment of patients from each center will be on a first-interviewed-and-demographic-form-completed basis. The 1,400 questionnaires from HbSS/HbS β^0 patients will be further divided into the following strata:

- 200 subjects ages 5 to 9.9 years
- 400 subjects ages 10 to 14.9 years
- 400 subjects ages 15 to 24.9 years
- 400 subjects age 25 years and older.

The 250 HbSC and HbS β^+ questionnaires will be from persons 15 years of age and older and in any proportion of those diagnoses. Each center will be encouraged to enroll all patients that they have available up to 25% of the total number of respondents in each age range until the total desired is reached. When a center enters 25% of the total patients in one age stratum, or the grand total of participants for an age stratum is reached, no further

questionnaires will be accepted by the SDMC from that center in that age stratum. Centers will be encouraged to continue to enter patients in other age strata.

We will estimate the priapism prevalence and its 95% two-sided confidence interval for 4 age groups: 5 to 9.9 years, 10 to 14.9 years, 15 to 24.9 years, and 25 years and older. To estimate the necessary sample sizes for each age group, we used the formula:

$$n = \frac{(2 \cdot 1.96)^2 (p)(1-p)}{(w)^2}$$

where w is the total confidence interval width, and p is the expected prevalence.

If an age group has a priapism prevalence of 15%, then 196 completed interviews are needed for a 0.10 wide 95% two-sided confidence interval for the estimated proportion of patients with priapism among patients with sickle cell disease. A group that has a priapism prevalence of 30% will need 323 completed interviews; 385 completed questionnaires are needed for a group that has a priapism prevalence of 50%. We would like to conduct more interviews in each category than these predictions suggest to be sure of obtaining adequate data to achieve the aims of this study. Specifically, we seek to obtain 1,400 complete interviews with accompanying demographic data according to the age distribution noted earlier. With the planned sample size and anticipated observed proportion of patients with priapism in each age range, each of the 4 two-sided 95% confidence intervals should have a total width of 0.10. The specified sample sizes for the 15 to 24.9 years strata and 25 or older may not be reached, in such a case the two-sided 95% confidence interval will have a total width larger than 0.10.

Tabulation of the responses to the questions on the patient survey and correlation with information collected on the demographic sheet will provide the data necessary to accomplish the primary and secondary outcome measure #1. The responses from the 250 HbSC/HbS β^+ participants will not be used to establish a prevalence of priapism per se, rather interesting characteristics including absence of episodes will be compared to those reported by the HbSS/HbS β^0 group. Participation of patients in the questionnaire will allow attainment of secondary outcome measure #3. The combined sample size and division between participating centers will allow us to estimate prevalence aggregating across all sickle cell centers as well as look at differences between centers. With the planned sample size and anticipated observed proportion of patients with priapism in each age range, a two-sided 95% confidence interval based on a normal approximation will have a total width of 0.10.

Sites will be requested to track rates of and reasons for refusal and basic demographic data which will not be reported except in an aggregate format.

10.2 Statistical Methods

In each age strata, an unadjusted 95% confidence interval of the priapism prevalence based on a normal approximation will be used to accomplish the primary outcome measure #1. Numerical summaries and frequency tabulation of the responses to the questions on the patient survey and information collected on the demographic sheet will provide the data necessary to accomplish the secondary outcome measure #1. Descriptive comparisons between the 1,400 HbSS/HbS β^0 and the 250 HbSC/HbS β^+ responses will accomplish secondary outcome measure #2. Tabulating the number of patients who did not know about priapism at start of study will accomplish the secondary outcome measure #3. The completed database will identify patients that are available for future clinical trials of secondary prevention and accomplish the secondary outcome measure #4. In addition to the primary objective and three secondary objectives, exploratory analyses will be completed to identify any differences between Ccenters and disease diagnoses.

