6 STUDY OBJECTIVES AND PURPOSE

Primary Hypothesis:

Priapism is a common complication of sickle cell disease. In 5- to 10-year-old patients, it is hypothesized that the prevalence of priapism is 10%. In 10- to 15-year-old patients, it is hypothesized that the prevalence of priapism increases to 20%. In patients over 15 years old, it is hypothesized that the prevalence of priapism reaches 30%.

Objectives:

1. Enumerate the cross-sectional prevalence, demographics, and common clinical characteristics of priapism in males with sickle cell disease among the CSCC patient population.
2. Identify patients eligible for randomized clinical trials of promising secondary prevention strategies.

Specific Aim(s):

1. To conduct a questionnaire survey of 1,400 males with sickle cell anemia (HbSS) and sickle beta zero thalassemia (HbS β^0) 5 years of age and older in order to determine the prevalence (frequency) and characteristics (number and pattern of episodes, cause or precipitating event, treatment, and outcome) of priapism.
2. To survey 250 additional males with other forms of sickle cell disease with the same instrument and describe the occurrence and characteristics of priapism experienced.
3. To develop a structured educational brochure about priapism for patients with sickle cell disease.
4. To identify the number of patients with recurrent priapism potentially eligible for randomized clinical trials of secondary prevention strategies.

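### The normal-approximation interval fixed for the primary outcome covers about 94%, not 95%, in the 5 to 9.9 year stratum, with misses mostly on the low side; a Wilson interval repairs this at no cost.

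*Protocol*

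**What the plan says.** Section 10.2 of the Protocol fixes the method for its only primary outcome. For each age stratum separately, an unadjusted 95% "confidence interval of the priapism prevalence based on a normal approximation will be used to accomplish the primary outcome measure #1". Section 10.1 sets the level, the sidedness and the groups: "We will estimate the priapism prevalence and its 95% two-sided confidence interval for 4 age groups". It also gives the sample-size formula, "where w is the total confidence interval width, and p is the expected prevalence", and says that with the planned numbers "a two-sided 95% confidence interval based on a normal approximation will have a total width of 0.10".

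The smallest stratum is "200 subjects ages 5 to 9.9 years"; each of the other three has 400, for example "400 subjects ages 10 to 14.9 years". For the youngest group Section 6 states: "In 5- to 10-year-old patients, it is hypothesized that the prevalence of priapism is 10" per cent. It hypothesizes 20% for ages 10 to 15 and 30% above 15.

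Differences between Centers are mentioned in Sections 10.1 and 10.2, in the latter as exploratory. No interval method is named for them.

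**The concern.** The Wald interval is centred on the observed proportion and takes its standard error from that same proportion. When the true prevalence is low, a sample that happens to have few events gives both a low centre and a short interval. The interval then misses the truth from below more often than the nominal 2.5%. The 5 to 9.9 year stratum has the smallest sample and the lowest hypothesized prevalence of the four, about 20 expected events, so any effect should show there first.

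At stake is whether the stated 95% is true for that stratum, and whether its upper limit understates how common priapism may be in the youngest boys. The method is written into the Protocol, so this is a choice that can be judged and not a detail left open.

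**Working it through.** **Inputs.** Stratum sizes of 200 and 400 and the width formula come from Section 10.1, the interval method from Section 10.2, and the prevalences of 10, 20 and 30% from Section 6.

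**Step 1: reproduce the plan's own figures.** The formula is n = (2 × 1.96)² p(1 − p) / w², with w = 0.10 and (2 × 1.96)² = 15.3664.
- p = 0.15: 15.3664 × 0.1275 / 0.01 = 195.9, rounded up to 196.
- p = 0.30: 15.3664 × 0.21 / 0.01 = 322.7, rounded up to 323.
- p = 0.50: 15.3664 × 0.25 / 0.01 = 384.2, rounded up to 385.

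All three match. Solved for w, the formula is w = 2 × 1.96 × √(p(1 − p)/n), the Wald width. This confirms which normal approximation is meant.

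**Step 2: formulas.** With p̂ = x/n and z = 1.96:
- Wald: p̂ ± z√(p̂(1 − p̂)/n).
- Wilson: [p̂ + z²/(2n) ± z√(p̂(1 − p̂)/n + z²/(4n²))] / (1 + z²/n).
- Exact coverage at (n, p): the sum of the binomial probabilities of all x from 0 to n whose interval contains p. Misses are split into intervals wholly below p and wholly above p.

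**Step 3: the single planning point.** At n = 200 and p = 0.10, Wald covers 92.7% (5.7% wholly below, 1.6% wholly above) and Wilson 95.6%. This value should not be read on its own. With x = 13 the Wald upper limit is 0.065 + 1.96 × √(0.065 × 0.935/200) = 0.0992, just under 0.10, and that one outcome carries about 2.5% of the probability. At p = 0.099 it is covered and Wald coverage is 95.0%. At p = 0.10 Wald covers 95.0% with n = 198 and 94.9% with n = 196.

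**Step 4: average the oscillation out.**

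| Range | Wald coverage | Wald wholly below / above | Wilson coverage | Wilson wholly below / above |
|---|---|---|---|---|
| n = 200, 181 values of p from 0.06 to 0.15 | 93.9% (min 91.1%) | 4.7% / 1.4% | 95.1% (min 93.8%) | 1.9% / 3.0% |
| p = 0.10, n = 180 to 220 | 94.0% | 4.7% / 1.3% | 95.1% | 2.0% / 3.0% |

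Wald is below 95% at 89% of the values in the first row and at 93% of those in the second. The lopsidedness remains where total coverage looks fine: at n = 200 and p = 0.08 Wald covers 95.3%, with misses of 3.7% below and 1.0% above.

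**Step 5: what a reader of the results would see.** Take 20 events in 200.
- Wald: 0.10 ± 1.96 × √(0.09/200) = 0.10 ± 0.0416, or 5.8 to 14.2%.
- Wilson: the centre is (0.10 + 3.8416/400)/(1 + 3.8416/200) = 0.1075 and the half-width 0.0419, or 6.6 to 14.9%.

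The widths are 0.0832 and 0.0837. Expected widths at n = 200 and p = 0.10 are 0.0826 for Wald and 0.0832 for Wilson.

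**Step 6: the other strata.** At n = 400 Wald covers 94.6% at p = 0.20 and 95.0% at p = 0.30, and about 94.8% averaged over nearby prevalences. There is no material shortfall.

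**The case against.** The best reply is that this hardly matters. A normal approximation is conventional with about 20 expected events in the smallest stratum and 80 to 120 in the others, and it matches the sample-size formula. The survey is descriptive, with no test or decision threshold tied to a limit. Section 7.2 already concedes ascertainment bias of unknown direction, and Section 10.1 concedes recall bias in adults. Against these, a shift of less than one percentage point in a limit is small. All of this stands, and it sets the weight of the point.

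Wilson is also not better everywhere. At n = 200 and p = 0.15, the prevalence behind the figure of 196, it covers 94.1% against 94.4% for Wald. Over 6 to 15% Wald equals or beats it at about 24% of values. Its misses lean slightly the other way, 3.0% above against 1.9% below. That stands too: the gain is an average of about 1.1 points and a better balance, not an improvement at every prevalence.

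Three stronger readings are tempting, and the Protocol does not support them.
- **That coverage in the youngest stratum is 92.7%, so that Wilson gains three points.** Step 3 shows that a change of 0.001 in p, or of 2 in n, removes most of that gap.
- **That the plan's interval breaks down at Center level.** Section 10.2 names the method for age strata only. Cell sizes by Center are not given beyond a 25% cap per Center and stratum. If Wald were carried over, an assumed 20 boys per Center at 10% would give 87.6% coverage, and a zero-width interval in 12.2% of samples. That is a hypothetical and not something the plan prescribes.
- **That under-enrolment will make it worse.** Section 10.1 expects possible shortfalls in the two oldest strata. At their hypothesized 30%, Wald averages 94.4% even at n = 100 (over p = 25 to 35%).

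None of this removes the average shortfall and the one-sidedness in the 5 to 9.9 year stratum.

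**Conclusion.** The point holds for one stratum of four. With about 200 boys aged 5 to 9.9 years and a true prevalence near the hypothesized 10%, the prescribed interval covers on average about one point less than stated. Its misses fall below the truth more than three times as often as above it (4.7% against 1.4%). The result assumes independent binomial responses and a true prevalence between 6 and 15%; it takes no account of clustering by Center.

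The planned sample sizes are unaffected. The importance is minor, and the case for acting is that the better interval costs nothing.

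**What to change.** In Section 10.2, name the Wilson score interval in place of the normal approximation for the age-stratum prevalences. Use it in all four strata for consistency, although only the youngest gains noticeably. The formula and the width statement in Section 10.1 can stay as planning approximations; at n = 200 and p = 0.15 the expected width is 0.0985 with either method.

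If Center-level prevalences are to be reported, add that the Wald interval will not be used for such small cells.

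The cost is a change of wording in the analysis section: no extra subjects, time or data items.

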7.1.1 Primary and Secondary Endpoints

Primary Outcome:

Enumeration of the prevalence of priapism in males with sickle cell anemia and sickle beta zero thalassemia.

Secondary Outcome Measures:

1. Characterization of priapism in males with sickle cell anemia with reference to time of onset, duration of events, frequency of episodes, precipitating or associated activities, treatment modalities used, and outcome of treatments.
2. Descriptive comparison of the prevalence of priapism in males with sickle cell anemia to that described in older patients with other sickle hemoglobinopathies.
3. Assessment of general patient and parent understanding of priapism as a complication of sickle cell disease gained from completion of protocol.
4. Enumeration of patients available for clinical trials of secondary prevention.

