8.1 Inclusion Criteria

Subjects who meet all of the following criteria are eligible for enrollment into the study:

1. Subject or parent/guardian gives written informed consent.
2. Male with or sickle cell anemia or sickle beta zero thalassemia 5 years of age or over
- **OR** -
Male with sickle beta plus thalassemia or sickle hemoglobin C disease 15 years of age or over.
3. Subject and/or parent/guardian able to communicate adequately with the interviewer.

Subjects currently taking hydroxyurea, undergoing chronic transfusion, or participating in other research trials including those involving agents such as arginine are eligible for the study if all other entry criteria are met.

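### Secondary outcome 2 compares HbSS/HbSβ0 males aged 5 and over with HbSC/HbSβ+ males aged 15 and over, so a planned age difference is mixed into the genotype comparison

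*Protocol*

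**What the plan says.** Section 7.1.1 defines secondary outcome 2 as a "Descriptive comparison of the prevalence of priapism in males with sickle cell anemia to that described in older patients with other sickle hemoglobinopathies". Section 10.2 says how it will be met: "Descriptive comparisons between the 1,400 HbSS/HbS β^0 and the 250 HbSC/HbS β^+ responses will accomplish secondary outcome measure #2".

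The two groups are recruited over different age ranges. Section 8.1 admits the first group as follows: "Male with or sickle cell anemia or sickle beta zero thalassemia 5 years of age or over". Section 10.1 divides its 1,400 into four age strata. Two of them lie below 15: "200 subjects ages 5 to 9.9 years" and "400 subjects ages 10 to 14.9 years". The other two, 15 to 24.9 years and 25 years and over, have 400 each. For the second group, section 10.1 states: "The 250 HbSC and HbS β^+ questionnaires will be from persons 15 years of age and older and in any proportion of those diagnoses". It sets no age quotas within that range.

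Section 6 gives the primary hypothesis: prevalence of 10% at 5 to 10 years, 20% at 10 to 15 years and 30% above 15 years. No section restricts, stratifies or standardises the genotype comparison by age.

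**The concern.** Age is the factor that the protocol itself expects to drive prevalence, and the two genotype groups differ in age by design. A contrast of the full 1,400 with the 250 therefore combines any genotype effect with an age effect of known direction. The boys under 15 lower the HbSS/HbSβ0 figure and have no counterpart in the other group. A true excess in HbSS/HbSβ0 would look smaller than it is, and a small excess could disappear or reverse.

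The result has a possible use. Section 10.1 expects the analysis of the 250 to suggest whether these genotypes belong in later intervention trials. A description that makes HbSC/HbSβ+ look closer to HbSS/HbSβ0 than it is at the same age would be a poor guide for that purpose.

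**Working it through.** **The plan's own figures.** The protocol gives no number for the genotype comparison. Its sample-size formula in section 10.1, n = (2 × 1.96)² p(1 − p)/w² with w = 0.10, reproduces:
- p = 0.15: 15.3664 × 0.1275/0.01 = 195.9, rounded up to 196.
- p = 0.30: 15.3664 × 0.21/0.01 = 322.7, rounded up to 323.
- p = 0.50: 15.3664 × 0.25/0.01 = 384.2, rounded up to 385.

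The problem is therefore not in the sample-size arithmetic.

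**Inputs.** The HbSS/HbSβ0 quotas are 200, 400, 400 and 400 (section 10.1). The hypothesised prevalences are 10%, 20% and 30% (section 6), with the 30% applied to both strata aged 15 and over. The HbSC/HbSβ+ group has 250 subjects, all 15 or over.

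**Expected HbSS/HbSβ0 prevalence.**
- All ages: (200 × 0.10 + 400 × 0.20 + 400 × 0.30 + 400 × 0.30)/1,400 = (20 + 80 + 120 + 120)/1,400 = 340/1,400 = 24.3%.
- Age 15 and over: (120 + 120)/800 = 240/800 = 30.0%.
- Gap: 30.0 − 24.3 = 5.7 points.

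**Effect on the comparison.** Let q be the HbSC/HbSβ+ prevalence. The difference as written is 24.3 − q, and the age-comparable difference is 30.0 − q. The first is always 5.7 points below the second, whatever q is. The protocol gives no value for q, so the values below are assumptions that show the range.

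| Assumed q | Difference at age 15 and over | Difference as written |
|---|---|---|
| 30% (no genotype effect) | 0 | −5.7 |
| 25% | +5.0 | −0.7 |
| 20% | +10.0 | +4.3 |
| 15% | +15.0 | +9.3 |

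**Sensitivity of the 5.7 points.**
- Section 10.1 allows that the two older strata may not fill. If they fill to 75% (600 subjects), the full group shows (100 + 180)/1,200 = 23.3%, a gap of 6.7 points. At 50% (400 subjects) it shows (100 + 120)/1,000 = 22.0%, a gap of 8.0 points.
- If the three prevalences used for sample size are assigned to the strata as 15%, 30%, 50% and 50% (an assumption), the full group shows (30 + 120 + 200 + 200)/1,400 = 39.3% against 50%, a gap of 10.7 points.
- If prevalence did not vary with age, the gap would be zero, but that contradicts section 6.

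**The case against.** The strongest reply is that this is a descriptive comparison which the protocol deliberately keeps modest. Section 10.1 says that the 250 will not support a statistical estimate of prevalence and that their responses serve mainly for description. The planned HbSS/HbSβ0 prevalence estimates are per age stratum, so no pooled 24.3% is specified anywhere. The references to the 1,400 and the 250 may simply be labels for the two cohorts. The endpoint itself says that the comparators are older, so a reader is warned. The layout of a descriptive table could also be left to a separate analysis plan, which is not at hand.

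Part of this stands. No interval or test between genotypes is planned, so a reader should not infer that the age imbalance turns a significant result into a non-significant one or the reverse. The documents also do not say that inclusion in later trials will be decided on this contrast; section 10.1 says only that the analysis will suggest a rationale.

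The core is not answered. Confounding shifts a descriptive difference as much as a tested one. Section 7.1.1 still calls the outcome a comparison of prevalence, and section 10.1 still compares the groups on the absence of episodes. Calling the comparators older acknowledges the imbalance without dealing with it. Section 10.2 does not leave the comparison group open: it names all 1,400.

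A reader might extend the point to Centers, since section 10.2 also says that "exploratory analyses will be completed to identify any differences between" Centers and diagnoses. The protocol gives no method for that analysis and no age mix by Center, so there is no crude Center comparison to fault. The same holds for the planned correlations with other complications of the disease, for which no method is stated.

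**Conclusion.** The point holds, at moderate severity. As worded, secondary outcome 2 sets a group with 43% under 15 against a group with none under 15. On the protocol's own hypotheses, this shifts the difference by 5.7 points against HbSS/HbSβ0. That size assumes that the quotas are met, that the 10%, 20% and 30% prevalences are right, and that the 30% applies equally to both older strata. Under-filling of the older strata or a steeper age gradient would increase it. The direction needs only that prevalence rises with age.

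A reader might infer that the main prevalence results are compromised. They are not: section 10.2 estimates the primary outcome within each age stratum. The defect is confined to the genotype comparison and can be corrected from data that the study already collects.

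**What to change.** In section 10.2, state that secondary outcome 2 compares the 250 HbSC/HbSβ+ subjects descriptively with the HbSS/HbSβ0 subjects aged 15 and over (800 planned), shown separately for 15 to 24.9 years and for 25 years and over. The split is needed because the 250 have no age quotas, so the two groups could still differ in age above 15. A formal age-adjusted estimate is not needed for a descriptive outcome.

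The cost is one or two sentences. Enrolment and data collection do not change, since age already defines the strata. The HbSS/HbSβ0 comparison group falls from 1,400 to 800. As an illustration only, since no interval is planned, with an assumed 20% in HbSC/HbSβ+ the 95% half-width of the difference would be:
- 800 versus 250: 1.96 × √(0.30 × 0.70/800 + 0.20 × 0.80/250) = 5.9 points.
- 1,400 versus 250: 1.96 × √(0.243 × 0.757/1,400 + 0.20 × 0.80/250) = 5.4 points.

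The loss of about half a point in precision is small beside the 5.7-point shift that it removes.
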